The current study aims to pilot test the feasibility and acceptability of Problem Management Plus for Immigrants (PMP-I) among Bhutanese immigrants 18 years and older living in Massachusetts.

Aim 1: Adapt and culturally modify PMP to develop PMP-I as a family-based preventative intervention.

- a) Develop a training guide and intervention curriculum;
- b) Obtain iterative feedback about the format, ease of use, and implementation barriers from participants, facilitators, and community members.

Aim 2: Test the feasibility, acceptability, and preliminary outcomes of PMP-I with trained community facilitators.

- a) Assess i) recruitment, session attendance, and retention rates and program acceptability using checklists from participants; ii) feasibility of measures for assessing inclusion/exclusion, the fidelity of intervention delivery, mediators of response, and outcomes using checklists from facilitators; and iii) barriers and facilitators of intervention using interview and focus group discussion with participants and facilitators.
- b) Test preliminary effects of PMP-I vs. talk program with community support services pamphlets (CSS) using a small randomized pilot trial (N=116 families; 58 families per intervention and control) on perceived stress, anxiety and depressive symptoms (primary), physiological stress assessed in hair cortisol (secondary), and self-efficacy and coping strategy, family wellbeing, and social networking (targets), with assessments at baseline, post-intervention, and 3-month post-intervention.
- c) Evaluate the relationships between targets and outcomes and explore mediators (e.g., coping) of intervention-outcome relation.

Design and Outcomes

Study design:

This mixed-methods study will incorporate a two-arm randomized controlled feasibility trial and qualitative evaluation of PMP-I intervention's acceptability to a range of stakeholders.

Allocation: Randomized

Intervention Model: Parallel Assignment

Masking: None

Primary purpose: Prevention

Outcomes:

Primary Outcome

Perceived stress: The 10-item Cohen Perceived Stress Scale (PSS)¹ will be used to assess perceived stress at baseline, post-intervention, and three-month post-intervention. The PSS uses a 5-point Likert scale (ranging from 0, “never” to 4, “very often”) to assess psychological stress experienced during the past month, including the extent to which situations felt unpredictable, uncomfortable, and overwhelming.

Anxiety and Depressive symptoms: The Hopkins Symptom Checklist-25 (HSCL-25)² will be used to measure anxiety and depressive symptoms experienced over the past month at baseline, post-intervention, and three-month post-intervention. It is composed of a 10-item subscale for anxiety and a 15-item subscale for depression, with each item scored on a Likert scale from 1 (not at all) to 4 (extremely).

Secondary outcome

Physiological stress: Cortisol hair-test (average hormone levels over the past three months) will be used as a biomarker to measure physiological stress. Neuroendocrine indicators, such as cortisol, are effective stress biomarkers because they are the first to respond to a given stressor and coordinate the physiological response of other bio-physiological systems.

Interventions and Duration

Study Arms:

Experimental: Problem Management Plus for Immigrants (PMP-I) at family settings

Active Comparator: Talk program with Community Support Service Pamphlet (CSS)

Assessment:

Baseline, Post-Intervention, and 3-month Post-Intervention

Intervention:

PMP-I is a 5-week, peer-led, culturally tailored psychoeducation, behavioral activation, and problem-solving (90 minutes), breathing and yoga intervention (90 minutes) in a family setting. PMP-I will use a structured approach, including once a week, face-to-face sessions, breathing, yoga practice, homework that includes recording activities, rebuilding individual skills, or learning new skills to reduce stress.

- 1. Managing Stress:** Breathing and yoga practices, stress-management sessions, and behavioral activation exercises to strengthen positive coping strategies.
- 2. Managing Problems:** Practice exercises to identify the problems, develop solutions, and plan a strategy to carry out those solutions.
- 3. Behavior Activation:** Communication skill sessions and practice exercises to identify and carry out pleasant tasks.
- 4. Strengthening Social Support:** Social skills session and practice exercise to identify social support.
- 5. Staying Well:** Make a plan that helps to create a supportive family environment.

Sample Size and Population

This study will be conducted among 226 Bhutanese adults settled in Massachusetts.

STUDY TEAM ROSTER

Principal Investigator: [name]., MPH, MPHC, CGM
Assistant Professor, College of Nursing, [name], University Massachusetts Amherst, MA, 01003
Email: [contact]
[contact]

Co-Investigator: [name].

1 STUDY OBJECTIVES

1.1 Hypothesis: Immigrants in the Problem Management Plus for Immigrants (PMP-I) will have significantly lower stress and anxiety/depressive symptoms than immigrants in the talk program with Community Support Service pamphlets (CSS).

1.2 Objective: The current study aims to pilot test the feasibility and acceptability of PMP-I among Bhutanese immigrants 18 years and older living in Massachusetts.

Aim 1: Adapt and culturally modify PMP to develop PMP-I as a family-based preventative intervention.

- a) Develop a training guide and intervention curriculum;
- b) Obtain iterative feedback about the format, ease of use, and implementation barriers from participants, facilitators, and community members.

Aim 2: Test the feasibility, acceptability, and preliminary outcomes of PMP-I with trained community facilitators.

- a) Assess i) recruitment, session attendance, and retention rates and program acceptability using checklists from participants; ii) feasibility of measures for assessing inclusion/exclusion, the fidelity of intervention delivery, mediators of response, and outcomes using checklists from facilitators; and iii) barriers and facilitators of intervention using interview and focus group discussion with participants and facilitators.
- b) Test preliminary effects of PMP-I vs. talk program with community support services pamphlets (CSS) using a small randomized pilot trial (N=116 families; 58 families per intervention and control), on perceived stress, anxiety and depressive symptoms (primary), physiological stress assessed in hair cortisol (secondary), and self-efficacy and coping strategy, family wellbeing, and social networking (targets), with assessments at baseline, post-intervention, and 3-month post-intervention.
- c) Evaluate the relationships between targets and outcomes and explore mediators (e.g., coping) of intervention-outcome relation.

2 BACKGROUND AND RATIONALE

2.1 Background

Traumatic experiences and everyday stressors during and after migration contribute to the emergence of depression and other mental health problems among immigrants.³⁻¹⁵

Immigrants living in the U.S. are more vulnerable to depression, anxiety, and psychological distress than the general population.^{3, 7, 9, 10, 16-19} Although mental health treatments help alleviate the social and economic costs of mental disorders, immigrants underutilize such services.²⁰⁻²² For instance, Asian Americans use fewer mental health-related services compared with the general population; only 8.6% of Asian Americans sought any mental health-related services versus 17.9% of the general population in the National Comorbidity and Replication study.²² In the National Latino and Asian American Study, only 8.5% (179/2095) of the total national sample of Asian Americans and 36.1% (68/188) of individuals who had a probable diagnosis of a psychiatric disorder sought mental health-related services.²⁰ Research suggests that culturally tailored, community-oriented strategies are needed to overcome barriers and prevent mental illness.²³ Specifically, the CDC recommends using a non-clinical, community support approach to prevent mental illness among refugees resettled in the U.S.²⁴

Stress resulting from attempts to integrate into a new culture while maintaining one's own culture takes a heavy toll on newly settled immigrants' mental health.²⁵ Immigrants' risk for mental health problems increases during their acculturative process due to exposure to multiple stressors such as adjusting to a new culture with limited language^{26, 27} and socio-cultural skills, and a lack of culturally-mediated and protective social support resources.²⁸⁻³⁰ Language problems can impede social and professional integration, reduce self-esteem, create social isolation, and increase stress. Perceived stress of acculturation^{14, 15, 31-33}, or discrimination^{4, 34} is strongly associated with immigrants' psychological distress. Previous studies point to difficulties immigrants encounter in various spheres of daily life such as acculturation to employment,³⁵⁻³⁷ housing,³⁵⁻³⁷ and education;^{35, 37} changes to family roles and obligations;³⁸ inadequate parenting skills,³⁸ and weak bonds in family and social ties.³⁸

Bhutanese immigrants are one of the most disadvantaged newly settled populations residing in inner cities in the U.S. In Hampden County, MA—consistently ranked the

poorest county in the state—there are approximately 4,000 Bhutanese. Our need assessment studies³⁹⁻⁴¹ found a high prevalence of depression (23.8%), anxiety (34.5%), and perceived high stress (38.1%) among Bhutanese immigrants living in Western MA. Unlike other South Asian immigrants, Bhutanese immigrants come from rural farming backgrounds and typically are illiterate. It is hard for them to learn English quickly and thus be able to communicate and work in the U.S. Limited literacy skills impede learning other social skills required to adapt to a new culture. We found that Bhutanese tend to rely exclusively upon their own ethnic, cultural, and religious supports and are less willing to explore and use resources and services from the host community. Their culture of interdependence impedes them from exploring their host culture and engaging in social and recreational activities outside of their own culture, leading to social isolation. One of the most prevalent community concerns is coping with the overall lack of support and isolation found in a new country. Lack of motivation and confidence to learn new skills and feelings of social isolation are the major stressors highlighted by the Bhutanese immigrants living in Western MA.⁴⁰ Understanding these cultural dynamics are essential for designing culturally tailored mental health promotion program.

2.2 Study Rationale

Existing interventions are primarily based on treatment models to improve access to and quality of care for immigrants with diagnosed mental health problems;^{42, 43} however, culturally tailored, preventative behavioral interventions aimed at preventing or reducing mental health problems are limited. For prevention, a culturally tailored intervention that addresses multiple psycho-socio-cultural stressors holds the most promise.⁴⁴⁻⁴⁷ Problem Management Plus (PMP) is a low-intensity evidence-based psychological intervention developed by the World Health Organization that can be delivered by trained laypeople.^{48,}⁴⁹ PMP systematically teaches four strategies: stress management through breathing exercises, problem-solving, behavioral activation, and skills to strengthen social support at the individual level. The current study plans to adapt PMP to develop the PMP for Immigrants (PMP-I) for a family setting to address immigrant's multiple social and emotional stressors while adjusting to the United States' new multi-cultural environment. The rationale to adapt PMP is based on our intervention model that demands an integration

of social and emotional stressors; promising results of PMP; strong evidence of family and community ties in health care process; and growing consensus among community, scientists, and policymakers on the need for family-based care models that are sustainable. PMP-I is a 5-week, peer-led, culturally tailored mental health promotion program that includes psychoeducation, behavioral activation, problem-solving (90 mhnutes/session/weekly), breathing exercises, and yoga (90 minutes/session/weekly) in a family setting.

3 STUDY DESIGN

Study design: This mixed-methods study will incorporate a two-arm randomized controlled feasibility trial and qualitative evaluation of the acceptability of Problem Management Plus for Immigrants (PMP-I) intervention to a range of stakeholders.

Allocation: Randomized

Intervention Model: Parallel Assignment

Masking: None

Primary purpose: Prevention

Outcome Measures

[figure not shown]
Name: Anxiety & Depressive Symptoms

Type: Primary

Time Frame: Baseline, Post-intervention, 3-month Post-intervention

Brief Description: The Hopkins Symptom

Checklist-25 (HSCL-25)² will be used to measure anxiety and depressive symptoms experienced over the past month. It is composed of a 10-item subscale for anxiety and a 15-item subscale for depression, with each item scored on a Likert scale from 1 (not at all) to 4 (extremely). The scale was validated for use in Nepal with a clinical DSM-IV diagnosis of major depressive disorder. The sensitivity and specificity with a cutoff point

of 1.75 were 0.87 and 0.60, respectively, with an area under the curve of 0.79.⁵⁰ The HSCL-25 has widely been used in studies among refugees in other countries as well as Nepal. The HSCL-25 score was categorized into two groups: the cutoff score of 1.75; depressed (1.75 or more), and not depressed (below 1.75). The scale has high internal consistency for anxiety (Cronbach's $\alpha = 0.92$) and depression (Cronbach's $\alpha = 0.94$) in our previous study with the same population group.³⁹

Name: Perceived Stress

Type: Primary

Time Frame: Baseline, Post-intervention, 3-month Post-intervention

Brief Description: The 10-item Cohen Perceived Stress Scale (PSS)¹ will assess perceived stress. The PSS uses a 5-point Likert scale (ranging from 0, “never” to 4, “very often”) to assess psychological stress experienced during the past month, including the extent to which situations felt unpredictable, uncomfortable, and overwhelming. The items included in the PSS scale are easy to understand as it was designed for use with community samples with junior high school education. This scale has been widely used in diverse populations, including immigrants. The scale has high internal consistency (Cronbach's $\alpha = 0.80$) in our previous study with the same population group.³⁹ Items were summed to provide a total score with higher scores indicating greater perceived stress.

Name: Physiological stress

Type: Secondary

Time Frame: Baseline, 3-month Post-intervention

Brief Description: We will use the ELISA cortisol hair-test (average hormone levels over the past three months) as a biomarker to measure physiological stress. Neuroendocrine indicators, such as cortisol, are effective stress biomarkers because they are the first to respond to a given stressor and coordinate the physiological response of other bio-physiological systems. Biomarker measurement helps to overcome the limitations of self-report because it provides an objective marker of levels of stress. Hair samples will be processed in the neuroendocrine lab at UMass.^{51, 52} Sensitive and specific

enzyme immunoassay (Salmetrics) will be used for the analysis. The assay has intra- and inter-assay coefficients of variation of <10%. The cortisol distribution will be tested for normality, and if the data are not normal, they will be log-transformed before statistical analysis.

Study Location and Population:

Bhutanese adults resettled in Massachusetts, USA.

Study Arms:

Experimental: Problem Management Plus for Immigrants (PMP-I) at family settings (58 families)

Active Comparator: Talk program with Community Support Service Pamphlet (CSS) (58 families)

Intervention:

PMP-I is a 5-week, peer-led, culturally tailored psychoeducation, behavioral activation (90 minutes), breathing, and yoga intervention (90 minutes) in a family setting. PMP-I will use a structured approach, including a once-a-week face-to-face session, breathing, and yoga practices.

1. Managing Stress: Breathing and yoga practices, stress-management sessions, and behavioral activation exercises to strengthen positive coping strategies.

2. Managing Problems: Practice exercises to identify the problems, develop solutions, and plan a strategy to carry out those solutions.

3. Behavior Activation: Communication skill sessions and practice exercises to identify and carry out pleasant tasks.

4. Strengthening Social Support: Social skills session and practice exercise to identify some support.

5. Staying Well: Make a plan that helps to create a supportive family environment.

4 SELECTION AND ENROLLMENT OF PARTICIPANTS

4.1 Inclusion Criteria

We plan to include eligible adults aged 18 or older interested in participating in the study as primary study participants. This includes parents and their adult children aged 18 and above. At baseline, we will use our screening tool to identify individuals without significant depressive symptoms, as we aim to evaluate the effect of our intervention to prevent depression, rather than treat depression.

Eligibility criteria for our primary study participants include Bhutanese adults 18 years or older (both parents and children of each family) resettled in Massachusetts with a score 14 or below on the Patient Health Questionnaire (PHQ-9), a screening questionnaire for depression. Our statistical analysis will focus on data from primary study participants only with baseline PHQ-9 scores 14 or below. However, all other interested adult family members, both parents and their adult children, regardless of PHQ-9 score, will be invited to participate in our study, to maintain the confidentiality of each family member's mental health status within their family.

Besides, individuals with PHQ-9 screening score '15-19' (moderately severe depression) and '20-27' (severe depression) will be provided with feedback on their screening questionnaire outcomes confidentially. They will be encouraged to consult their primary health care providers. A field supervisor can provide the necessary support for setting up an appointment with primary health care providers and emergency services, as needed. A field supervisor also will make a follow-up home visit to monitor their mental health condition, as necessary.

4.2 Exclusion Criteria

Participants with clinically diagnosed mental disorders and those taking psychiatric medications for any mental health problems will also be encouraged to participate in the family-based intervention activities. However, we will not consider data from those participants with PHQ-9 scores 15 or above or diagnosed with mental health problems in our main statistical analysis.

4.3 Study Enrollment Procedures

Identifying survey participants

The PI has already established a strong network with the Bhutanese community and completed her needs assessment studies collecting determinants of a mental health problem through engaging community members in the research process. We will use an existing community network to spread the study information in coordination with church leaders, community research assistants (RAs), and supervisors. PI will prepare an oral script including study objectives, eligibility criteria, intervention procedure, study and survey information, hair sample collection, and informed consent procedure. It will also distribute it to them to spread the study information. They will be requested to disseminate the information about the study purpose and process to their community in phone or in-person meetings in any of their gatherings, word of mouth, formal/informal discussions, and festivals to check-in for their interest to participate in the study. Interested participants will be requested to contact PI, RAs, and supervisors.

Recruiting survey participants

Community RAs from the local area will be mobilized to reach interested families to check their eligibility and make a list of eligible participants. Eligibility criteria for participants are: being Bhutanese adults 18 years or older resettled in Massachusetts with a score of 14 or below on the Patient Health Questionnaire-9, showing commitment to complete the intervention procedure, and giving informed consent to participate in the study. RAs will recruit interested eligible participants with their informed consent and will conduct a baseline survey. RAs will be asked to leave a note in the screening tool and screening log of reasons for ineligibility, such as a PHQ-9 score of more than 14 or any history of clinically diagnosed mental health problems or taking any medication related to mental health problems. RAs will also leave a note for non-participation of eligible candidates in the screening tool and screening log.

Randomizing study participants for intervention and control

We will randomly allocate selected families into intervention and control groups using a random sampling method after the baseline survey. We will randomly assign 116 interested

families (58 families per intervention and control) using a random number table. For random allocation, first, PI will prepare the sampling frame that lists interested families. Second, assign a number to each family in the sampling frame. Third, select 116 numbers using a table of random numbers. PI will request any interested community member to point one number in the random number table by closing his/her eyes. Since the selected families total 116, or three digits, we will choose only the first three digits of the number chosen as the first sampled family. Finally, we will choose other numbers moving down the first number column until all 116 families will be selected.

We will assign a random number selected at the first attempt for intervention and the second attempt for control. It means random numbers selected at odd attempts (first, third, seventh,) will be assigned for intervention and at even attempts (second, fourth, sixth...) for control. The sample elements corresponding to the selected random numbers become the sample. Procedures are in place for tracking the participants for intervention and follow-up (e.g., contact address and phone). RAs will visit selected families and brief them about study procedures, informed consent, and procedures to protect human subjects. All adult members of selected families who meet the inclusion criteria and give informed consent will be recruited for the study. We will follow up with all families randomized to either study arm. We will not follow up with participants if they decide to end their participation at a particular time point of our study. But, we will include their already collected data in our analysis. Given our strong community networks and mobilization of community RAs, we anticipate low attrition rates in practice. Ethical approval for our study will be obtained from the Institutional Review Board at UMass Amherst.

Recruitment of focus group discussion participants

PI will collect data on engagement, acceptability, and satisfaction of intervention delivery by conducting focus group discussions (FGD) with selected interested participants who are already enrolled in our study from the intervention group (30) upon intervention completion using a brief guide questionnaire. The participant will be eligible to attend the focus group discussion if they are already enrolled in our intervention group and have attended our mental health promotion program. RAs will inform participants about FGD

details verbally while implementing our mental health promotion program. We will recruit interested participants on a first-come-first-serve basis until we get enough participants.

Informed consent procedure

PI will prepare an informed consent document including an explanation on study background, rationale, screening criteria, inclusion and exclusion criteria, study setting, sample size, data collection and intervention procedures, study risks and benefits, privacy and confidentiality of personal information, National Institute of Mental Health Data Archive (NDA) data sharing policy, hair samples collection procedure, storage, and testing procedure, participant compensation, study policy, and study contact person details. PI will train community RAs and field supervisors about processes of taking informed consent from participants.

RAs will inform screening and study procedures to each participant using UMass Amherst IRB approved single informed consent form. A copy of the informed consent form will be provided to each participant for their review. If they want, RAs can read informed consent for them. Participants will be given enough time to review informed consent and ask questions if they have any confusion. RAs will make sure that participants understand about study procedure, privacy and confidentiality of private information, and data sharing policy of NDA. They will be reminded that their participation in the study is voluntary and free to leave the study without penalty. Once participants understand about study details, RAs will request them to do their signature or write their initials or fingerprint for those who cannot write their names in the two copies of the informed consent form before collecting their information. One copy of signed informed consent will be provided to each participant. We will not recruit any individuals who are unable to consent for themselves. The signed informed consent documents will be stored securely in the locked cabinet of the PI's office. (Please see the attached informed consent for details)

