Family satisfaction: Family satisfaction with various aspects of family functioning, including family closeness, flexibility, and communication will be measured using a 10-item family satisfaction scale.⁶⁰ A sample item from this scale is, “How satisfied are you with the degree of closeness between your family members.” Participants will be asked to respond on a 5-point Likert-type scale, ranging from *very dissatisfied (1)* to *extremely satisfied (5)*.

Randomization

Participants will be randomly assigned to intervention and control groups within 7-days of baseline survey completion. The first session of intervention will be delivered to the intervention and control groups within the seven days of baseline survey completion.

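### Arms alternate along an unconcealed table draw, and the sections disagree on whether consent and baseline come before the arm is known; if draws are rolling, some families' arms become guessable

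*Combined protocol and SAP*

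**What the plan says.** Section 4.3 sets out the method.

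- **The list.** "first, PI will prepare the sampling frame that lists interested families", and each family is then numbered.
- **The start.** "PI will request any interested community member to point one number in the random number table by closing his/her eyes".
- **The draw.** After that, "we will choose other numbers moving down the first number column until all 116 families will be selected".
- **The arms.** "random numbers selected at odd attempts (first, third, seventh,) will be assigned for intervention", and those "at even attempts (second, fourth, sixth...) for control". The stated result is 58 families per arm.

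On timing, the sections differ.

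- Section 4.3, opening of the randomisation text: "We will randomly allocate selected families into intervention and control groups using a random sampling method after the baseline survey".
- Section 4.3, after the draw is described: research assistants visit the selected families, explain the study and consent, and recruit the adults who qualify and agree.
- Section 6.2.2: "Participants will be randomly assigned to intervention and control groups within 7-days of baseline survey completion". The first session, in both arms, has the same limit.
- Section 6.1: the schedule marks randomisation in the Visit 1, Day 0 column together with baseline.

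Section 3 states that there is no masking. No section describes concealment of the sequence, or names anyone outside the PI and field team to hold it.

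**The concern.** Alternation is safe only while nobody can connect the next position in the sequence to a particular family. That holds when a complete list is drawn once. It weakens when families are drawn a few at a time, because anyone who has counted the draws so far knows which arm opens the next batch.

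The people who list, approach and enrol families here come from the same community and know many of them. The primary outcomes are self-reported and the trial is unmasked. If a likely arm can influence which family is put forward, or which adults in a family agree to join, the arms can differ in ways the analysis will not repair. The multilevel model in section 9.2 adjusts only for measured baseline variables that happen to differ significantly. The trial's stated purpose is to supply effect sizes for a larger trial, so any such bias would carry forward into that design.

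**Working it through.** **Inputs.** 116 families, 58 per arm, odd positions to PMP-I and even to control (section 4.3). Two to four adults per family (section 9.1). A 7-day limit from baseline to randomisation (section 6.2.2). Randomisation marked at Day 0 (section 6.1). I read an attempt as a successful selection, the reading that gives equal arms.

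**1. The plan's own split.** Positions 1 to 116 contain 58 odd and 58 even numbers, so alternation reproduces 58 and 58.

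**2. One draw from a complete list.** The random element is which family falls at which position. Any given family has probability 58/116 = 0.50 of either arm. This is valid 1:1 allocation.

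**3. Does one draw fit the 7-day limit?** Only if every family completes baseline within the same 7 days:

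- families: 116/7 = 16.6 a day;
- adults at two per family: 232/7 = 33.1 a day;
- adults at four per family: 464/7 = 66.3 a day.

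The documents give no recruitment period, rate or number of interviewers to set against this load.

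**4. If draws are split.** Let a batch contain b families in random order, with alternation continuing from the previous batch. The best guess for any family is the arm that opens the batch. It is right with probability ceil(b/2)/b.

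| Batch size | Chance of a correct guess |
|---|---|
| 1 | 1/1 = 1.00 |
| 2, or any even number | 0.50 |
| 3 | 2/3 = 0.67 |
| 5 | 3/5 = 0.60 |
| 9 | 5/9 = 0.56 |

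**5. Average over a recruitment period (assumed, since none is stated).** Take a Poisson number of families per draw with mean λ. The average chance of a correct guess is 0.5 + (1 − e^(−2λ))/(4λ), and the share of families drawn alone is e^(−λ).

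| Weekly draws over | λ | Correct guess | Drawn alone |
|---|---|---|---|
| 3 months (13 weeks) | 116/13 = 8.92 | 0.53 | about 0% |
| 6 months (26 weeks) | 116/26 = 4.46 | 0.56 | 1% |
| 12 months (52 weeks) | 116/52 = 2.23 | 0.61 | 11% |

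If the Day 0 mark is taken literally and families are drawn on the day of baseline, λ falls to 116/91 = 1.27 over 3 months and 116/364 = 0.32 over 12 months. The chance of a correct guess then runs from 0.68 to 0.87.

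**6. Order of consent and allocation.** This step needs no batching. The opening of the randomisation text in 4.3 puts the baseline survey, and therefore consent and screening, before allocation. The later sentences in 4.3 start from a list of interested families, draw them with their arms, and only then send research assistants to brief, consent and recruit. Both orders cannot hold. Under the second, an adult's decision to join, or an assistant's effort to recruit, can follow knowledge of the family's arm. The documents give nothing from which to size this effect.

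**The case against.** The strongest defence is that section 4.3 describes a single draw: one list, one start chosen with eyes closed, and a read down the column to the 116th family. Followed that way after baseline, it is sound randomisation, and the alternation does no harm. The PI organises the draw but does not choose the starting number. The Day 0 mark sits in a combined baseline, enrolment and randomisation column, so it may be only a visit label. Where consent and baseline do come first, staff could not use a predicted arm to keep out a family already enrolled. They could at most move it between batches, and the 7-day limit restricts that.

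Most of this stands, and it rules out a stronger reading. A reader might infer that the 7-day rule forces the draw into batches and that the next arm is then always known. The documents support neither step. They mention no batches and give no recruitment pace, so a single draw is demanding but not shown to be impossible. Certainty attaches to the next position in the sequence; a particular family's arm is certain only when it is drawn alone.

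The defence does not supply a concealment step, remove the conflict between a single draw and the 7-day limit, or explain the sentences in 4.3 that place consent and recruitment after the draw.

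**Conclusion.** The point holds in conditional form and should be corrected before enrolment.

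- **Established by the text:** strict alternation, no concealment, no independent holder of the sequence, and conflicting statements on the order and timing of consent, baseline and randomisation.
- **Likely but not established:** rolling draws. The inference rests on the load of about 17 families a day that a single draw inside one week would require.
- **Size if draws are rolling:** modest on average with weekly draws, larger with same-day draws. These averages depend on my assumed 3 to 12 months of recruitment, Poisson arrivals, and staff who keep count of earlier draws.
- **Independent of batching:** recruitment of adults after the arm is drawn, if the later sentences of 4.3 are followed. I put no number on it.

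**What to change.** Replace the table and alternation in 4.3 with a computer-generated family-level list, 1:1, in randomly varying blocks whose sizes are constrained to total 58 per arm. A co-investigator not involved in recruitment should hold it and release a family's arm only after all its enrolling adults have consented, been screened and completed baseline. Because the trial is unmasked, the end of a block can sometimes be deduced; varying the block size reduces this without removing it.

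At minimum, make one draw from a locked list of families whose baselines are complete, and state that no family or adult is added afterwards.

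Either way, reconcile 4.3, 6.1 and 6.2.2 so that they give one order and one timing for consent, baseline and randomisation. The 7-day limit is written per participant, so the text should say how it applies when adults in one family complete baseline on different days. The single-draw alternative in particular has to be squared with that limit.

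The cost is a few lines of SAS, which the plan already uses, and revised wording. No extra staff are needed. The real loss is the public draw with the community, which may have value for trust.
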